4.3 Selection of Study Population

4.3.1 Inclusion Criteria:

1. Histologically-confirmed adenocarcinoma of the pancreas, colon, or rectum.
2. Radiographic evidence of metastatic cancer of the colon or rectum
3. The subject has pancreatic cancer that is unresectable or already metastatic or colorectal cancer that has failed available treatment modalities.
4. For the pancreas subjects, he/she may be accepted without prior chemotherapy or with multiple therapies that have failed. The colon and rectal cancer subjects must have failed available chemotherapy/targeted regimens. There is no limit to the number of prior chemotherapeutic regimens.
5. The subject must have evidence of progressive disease defined as at least one of the following:
 - a. Progressive measurable disease: using conventional solid tumor criteria
 - b. Increasing tumor markers and/or activity on PET-CT SUV measurement
6. All clinically significant toxic effects (excluding alopecia) of prior surgery, radiotherapy, or hormonal therapy have resolved to \leq Grade 1 based on the NCI-CTCAE v 3.0, with the exception of peripheral neuropathy, which must have resolved to Grade \leq 2.
7. The subject has an Eastern Cooperative Oncology Group performance status (ECOG PS) of 0-2.
8. The subject has adequate hematologic function (minimum requirements: absolute neutrophil count [ANC] \geq 1500/mL, hemoglobin \geq 9 g/dL, and platelets \geq 100,000/mL).
9. The subject has adequate hepatic function (bilirubin \leq 1.5 times the upper limit of normal (ULN)), aspartate transaminase [AST] and alanine transaminase [ALT] \leq 3 times the ULN, or \leq 5 times the ULN, if liver metastases are present).
10. The subject has adequate renal function (creatinine \leq 2.0 mg/dL)
11. The subject has adequate coagulation function (an international normalized ratio [INR] \leq 1.5 and a partial thromboplastin time [PTT] \leq 5 seconds above the ULN [unless on oral anticoagulant therapy]). Subjects receiving full-dose anticoagulation therapy are eligible provided they meet all other criteria, are on a stable dose of oral anticoagulant or low molecular weight heparin (and if on warfarin have a therapeutic INR between 2 and 3).
12. The subject has a life expectancy of 6 weeks.
13. The subject is male or female and at least 18 years of age. For females of childbearing potential, a negative pregnancy test is required.
14. The subject agrees to use contraceptives (barrier method) while on study, if sexually active.
15. The subject has provided signed informed consent.

4.3.2 Exclusion Criteria:

1. Any condition (cardiovascular or other), making subject an unacceptably high anesthetic or surgical risk based on current anesthesia/general surgery standards.
2. Positive testing for HIV.
3. Cognitive impairment sufficient to render the subject incapable of giving informed consent.
4. Hypersensitivity reaction that, in the opinion of the investigators, poses an increased risk of an allergy to the macrobeads, particularly any known allergy to murine antigens or body tissues.
5. Surgical treatment or chemotherapy within three weeks of scheduled macrobead implantation or within four weeks of bevacizumab (or similar drugs), or radiation therapy within four weeks of scheduled macrobead implantation.
6. Investigational medications for their respective tumors within one month of baseline evaluation.
7. The subject has inadequate hematologic function (absolute neutrophil count [ANC] <1500/mL, hemoglobin <9 g/dL, and platelets <100,000/mL).
8. The subject has inadequate hepatic function [bilirubin >1.5 times the upper limit of normal (ULN)], aspartate transaminase [AST] and alanine transaminase [ALT] > 3 times the ULN, or > 5 times the ULN, if liver metastases are present).
9. The subject has inadequate renal function (serum creatinine > 2.0 mg/dL).
10. The subject has inadequate coagulation function (an international normalized ratio [INR] > 1.5 and a partial thromboplastin time [PTT] > 5 seconds above the ULN [unless on oral anticoagulant therapy]). Subjects receiving full-dose anticoagulation therapy are eligible provided they meet all other criteria, are on a stable dose of oral anticoagulant or low molecular weight heparin (and if on warfarin have a therapeutic INR between 2 and 3).
11. Hepatic blood flow abnormalities: portal vein hypertension and thrombosis; and/or large volume of ascites.
12. Concurrent cancer of any other type except skin cancer (excluding melanoma).
13. History of allergic reactions to mouse antigen.
14. The subject has an ongoing or active infection, symptomatic congestive heart failure, unstable angina pectoris, serious cardiac arrhythmias, (well-controlled atrial fibrillation, is permitted,) psychiatric illness/social situations that could interfere with the subject's ability to participate in the protocol, active bleeding.
15. As a result of the medical history, examination or blood testing, the investigator considers the subject unfit for the study.

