Exclusion Criteria:	
 1. Any condition (cardiovascular or other), making subject an unacceptably high anesthetic or surgical risk based on current anesthesia/general surgery standards. 2. Positive testing for HIV. 3. Cognitive impairment sufficient to render the subject incapable of giving informed consent. 4. Hypersensitivity reaction that, in the opinion of the investigators, poses an increased risk of an allergy to the macrobeads, particularly any known allergy to murine antigens or body tissues. 5. Surgical treatment or chemotherapy within three weeks of scheduled macrobead implantation or within four weeks of bevacizumab (or similar drugs), or radiation therapy within four weeks of scheduled macrobead implantation. 6. Investigational medications for their respective tumors within one month of baseline evaluation. 7. The subject has inadequate hematologic function (absolute neutrophil count [ANC] < 1500/mL, hemoglobin < 9 g/dL, and platelets < 100,000/mL). 8. The subject has inadequate hepatic function [bilirubin > 1.5 times the upper limit of normal (ULN)], aspartate transaminase [AST] and alanine transaminase [ALT] > 3 times the ULN, or > 5 times the ULN, if liver metastases are present). 9. The subject has inadequate renal function (serum creatinine > 2.0 mg/dL). 10. The subject has inadequate coagulation function (an international normalized ratio [INR] > 1.5 and a partial thromboplastin time [PTT] > 5 seconds above the ULN [unless on oral anticoagulant therapy]). Subjects receiving full-dose anticoagulation therapy are eligible provided they meet all other criteria, are on a stable dose of oral anticoagulant or low molecular weight heparin (and if on warfarin have a therapeutic INR between 2 and 3). 11. Hepatic blood flow abnormalities: portal vein hypertension and thrombosis; and/or large volume of ascites. 12. Concurrent cancer of any other type except skin cancer (excluding melanoma). 13. History of allergic reactions to mouse antigen. 14. The subject has an ongoing or active infection, symptomatic congestive heart failure, unstable angina pectoris, serious cardiac

PROTOCOL SYNOPSIS	

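### No entry criterion expressly requires recovery from chemotherapy or targeted-therapy toxicity, and the neutrophil and platelet limits as printed screen out almost nobody

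*Protocol*

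**What the plan says.** Protocol section 4.3.1, inclusion 6, sets the recovery rule: "All clinically significant toxic effects (excluding alopecia) of prior surgery, radiotherapy, or hormonal therapy have resolved to" Grade 1 or below on CTCAE v3.0, except that neuropathy may be up to Grade 2. The synopsis repeats the same list of prior treatments.

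Inclusion 4 describes what the population has received: "The colon and rectal cancer subjects must have failed available chemotherapy/targeted regimens. There is no limit to the number of prior chemotherapeutic regimens". Pancreatic subjects may enter untreated or after several failed therapies.

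Inclusion 8 sets minimum values for neutrophils, hemoglobin and platelets. Exclusion 7 in section 4.3.2 is meant as its counterpart: "The subject has inadequate hematologic function (absolute neutrophil count [ANC] <1500/mL, hemoglobin <9 g/dL, and platelets <100,000/mL"). The synopsis copies of both criteria use the same numerals and the same volume unit; its exclusion 7, for example, has "absolute neutrophil count [ANC] < 1500/mL, hemoglobin < 9 g/dL, and platelets < 100,000/mL".

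Exclusion 5 sets the interval after earlier treatment and rules out "Surgical treatment or chemotherapy within three weeks of scheduled macrobead implantation". It gives four weeks for bevacizumab or similar drugs and for radiation.

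**The concern.** A recovery rule should cover the treatments the population has had. This one leaves out the class that all colorectal subjects must have received. It does name hormonal therapy, which appears nowhere else in the text available of either document. The marrow limits might have filled part of the gap, but in the printed unit two of the three do no work.

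Implantation is abdominal surgery, and it is permitted once three weeks have passed since chemotherapy. What is at stake is mainly safety at entry. To a lesser degree it is the clean reading of toxicity in a trial without a concurrent control: under protocol 6.1 a condition present at entry becomes an adverse event if it worsens, under 6.5.1 a Grade 3 or higher reaction is a dose-limiting toxicity, and under 6.8 that opens a discussion of bead removal. SAP 7.2 will list whether each criterion was satisfied, so a subject with unresolved drug toxicity could be listed as meeting inclusions 6 and 8.

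**Working it through.** The documents give no derivation of these limits, so there is no sponsor calculation to reproduce. The check has four steps.

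**1. Inclusion 6 against inclusion 4.**
- Treatments whose toxicity must have resolved (inclusion 6): surgery, radiotherapy, hormonal therapy.
- Treatments colorectal subjects must have failed (inclusion 4): chemotherapy and targeted regimens, without limit on number.
- Overlap between the two lists: none.
- Colorectal subjects affected: all of them. Protocol Appendix 3, section 9, plans 74 patients with 40 pancreatic, so 74 − 40 = 34 colorectal. SAP 3.2 still has 20. The share is 100% on either count.

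**2. The unit.** With 1 mL = 1000 microlitres:
- Neutrophils: 1500 per mL ÷ 1000 = 1.5 per microlitre.
- Platelets: 100,000 per mL ÷ 1000 = 100 per microlitre.

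If the same numerals were meant per microlitre, the limits would be 1500 × 1000 = 1,500,000 per mL and 100,000 × 1000 = 100,000,000 per mL, exactly 1000 times the printed values. That intention is an assumption; the documents do not state it.

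**3. The logic of inclusion 8 and exclusion 7 as printed.** Take an illustrative subject (assumed values) with 400 neutrophils and 20,000 platelets per microlitre, that is 400,000 and 20,000,000 per mL.
- Hemoglobin 10 g/dL: 400,000 ≥ 1500, 10 ≥ 9 and 20,000,000 ≥ 100,000, so inclusion 8 is met. Exclusion 7 is not triggered.
- Hemoglobin 8 g/dL: inclusion 8 fails on hemoglobin alone. Exclusion 7 is still not triggered, because it joins its three conditions with *and* and only one is true.

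So the hemoglobin limit works, while the neutrophil and platelet limits pass counts about 267 times (400,000 ÷ 1500) and 200 times (20,000,000 ÷ 100,000) their printed value that are nonetheless low in this example.

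**4. The other numeric criteria.** Bilirubin, AST/ALT and creatinine measure liver and kidney function, whatever the cause of any abnormality. INR and PTT measure clotting. None counts neutrophils or platelets, so none replaces the two limits in step 2.

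**The case against.** The strongest reply is that other criteria protect the subject. Hemoglobin of at least 9 g/dL is an objective marrow limit in a working unit. Exclusion 5 imposes a washout. Exclusion 1 removes anyone whose anesthetic or operative risk is too high, exclusion 14 removes current infection and active bleeding, and exclusion 15 lets the investigator exclude on blood results. Section 5.1.1 requires the investigator or a designee to review all pretreatment results, including a blood count with differential and platelets. Section 5.1.2 bases the decision to implant on an overall assessment that includes routine blood work.

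This stands. A reader might infer that nothing in the protocol stops a subject with unresolved chemotherapy marrow toxicity, or that such a subject satisfies every criterion. The documents do not support either reading. But the washout is a time interval and not a recovery requirement, exclusion 14 acts once infection or bleeding is present, and exclusions 1 and 15 and the pre-implant review rest on judgement. They do not replace the grade-based and numeric rules the sponsor chose to write.

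Four further replies:
- *The unit is an obvious slip that no site would apply literally.* Probably so, and it may even be a misread symbol from the PDF conversion. Against that, all four copies agree and the micro sign survives elsewhere (section 4.2). The possibility cannot be ruled out from the text alone.
- *The* and *in exclusion 7 changes nothing.* Largely correct. Inclusion 8 separately requires each minimum and a subject must satisfy both lists, so this is editorial.
- *Attribution is barely harmed.* Mostly correct. Only conditions that worsen count as adverse events (protocol 6.1, SAP 11.1.2), the causality definitions in 6.3 weigh other causes, laboratory shifts run from baseline (SAP 11.1.3), and a dose-limiting toxicity opens only a discussion, which section 6.8 already starts at Grade 2. The accrual halt in 6.6 counts Grade 5 events only. No primary analysis is shown to change.
- *The effect on current enrolment is limited.* Protocol 7.1 says colorectal data have already been used to plan the next trial, and pancreatic subjects may enter without earlier chemotherapy. That reduces how many future entrants are affected but does not repair the criteria.

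**Conclusion.** The point holds in this form: no criterion expressly requires recovery from the toxicity of chemotherapy or targeted therapy, and no objective numeric criterion effectively screens for neutropenia or thrombocytopenia. Anemia is still screened, and the remaining protection is partial.

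Size: inclusion 6 omits the treatment class that 100% of colorectal subjects must have failed. The printed limits equal 1.5 neutrophils and 100 platelets per microlitre in all four places.

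Assumptions: that the source document shows the same unit as the text reviewed, and that candidates for this surgery almost never have counts below the printed limits. The factor of 1000 holds only if per microlitre was intended. The documents give no evidence that an unsuitable subject was enrolled because of this wording, and none is claimed.

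**What to change.** Three wording changes to the protocol, in both the synopsis and section 4.3:
- Reconcile the list of prior treatments in inclusion 6 with inclusion 4, and justify or remove the reference to hormonal therapy.
- Check the volume unit for neutrophils and platelets against the source document, and correct it in inclusion 8 and exclusion 7, four places in all.
- As an editorial matter, reconcile the *and* in exclusion 7 with inclusion 8, so that the two criteria are complements.

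No threshold or toxicity grade is proposed here; those remain for the sponsor. The blood counts are already taken at screening, so no test is added. The cost is an amendment, and a few candidates may wait longer or not be implanted.

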4.4 Screening to Exclude Subjects with Allergic Reactions to Mouse Antigens

All subjects eligible for this protocol will be screened by history of allergy to mouse antigens and with an available mouse allergen extract using skin testing initially to determine if a wheal and flare reaction is present. This will be carried out with Greer Laboratories, Inc. product # E2 (mouse epithelia). A positive reaction in the skin test will exclude the subject from this protocol. Positive control with histamine, and negative control with saline or glycerin will be done along with each murine skin test.

Baseline and follow-up Human Anti-Mouse Antibody (HAMA) levels will not be followed in this Phase 2 trial in as much as the experience in the Phase I trial indicated that HAMA is not a reliable indicator of reaction to mouse antigens. False positives are a major problem.

4.5 Treatments

4.5.1 Dosage Determination

Based on the animal studies conducted to date, as well as the Phase I human trial, a reasonable dosage range (number of beads implanted) is 8 macrobeads per kilogram of body weight. We know that 16 macrobeads per kilogram was also well tolerated in the Phase I human trial, but, at least with a single dose, this number was not seen to be any more effective than 8 macrobeads per kilogram. Given the fact, it is planned to carry out up to four implants (over approximately 12 months) in this Phase II trial, each implantation will be carried out at the 8 macrobeads per kilogram dosage.

4.5.2 Drug Labeling

Labeling will be defined as in BB-IND 10092.

4.6 Assessments

The objective of the proposed Phase II study of the RENCA macrobeads is, as stated above, to determine the human clinical efficacy of the cancer macrobeads in advanced pancreatic and colorectal cancer. Responses will be

assessed according to the usual categories of complete or partial response (with specification of percentage), and none/progression (with specification of percentage). Response assessment will be measured in terms of changes in volume of primary tumor and number of metastases as assessed by CT or MRI; tumor marker PSA, as well as the physician global clinical assessment; performance rating scale (Karnofsky or similar); quality of subject life as measured by the EORTC Quality of Life Scale. Alkaline phosphatase and lactic dehydrogenase will also be followed.

Other laboratory determinations to monitor subject response to the implantation of the macrobeads will include detection of inflammatory responses (CBC with differential WBC and platelet count, erythrocyte sedimentation rate, C-reactive protein, amylase, immunological changes, and cytokine production), RT-PCR (polymerase chain reaction) specific to e-MuLV DNA, plasma viremia, and antibodies to normal murine antigens.

A critical and unique addition to the endpoints for assessing efficacy will be, where possible, a careful search for and identification of the niches of cancer stem and other cells within the niche bodies of the tumors the macrobeads are being used to treat. Markers of the niche bodies used to identify them and study their state (numbers, integrity of surround blood vessels, degree of stress) will include HLA, CD44+, CD133+, p27, Ki67, and the Tunel assay for apoptosis. Determination of the presence or absence of circulating tumor cells will also be made. When possible/available, pathology specimens will be examined for cancer stem cell niches.

5 STUDY CONDUCT

5.1 *Schedule of Assessments*

Clinical procedures, laboratory tests, and other measures to be utilized (and their order and flow) in the trial are indicated in Appendix 2 (section 9.2), and below:

5.1.1 Study Days -28 to -1:

1. Pretreatment evaluations used to determine the subject's study eligibility must be completed within 28 days prior to implantation unless otherwise specified for particular individuals and circumstances
2. Written informed consent must be obtained prior to performing to any study-specific evaluations. Results of all pretreatment evaluations must be reviewed by the Principal Investigator or his/her designee to ensure that all eligibility criteria have been satisfied prior to subject implantation. There will be a complete review of the subject's cancer history and reports of tumor biopsies obtained. A series of clinical tests and procedures are to be performed at different intervals throughout the study.
3. All subjects must undergo the following pretreatment evaluations:
 - Medical history (including an assessment of baseline conditions, global clinical assessment, symptoms rating/severity assessment, quality of life scale [EORTC], pain scale assessment and activity of daily living rating)
 - Physical examination (including neurological examination, height and weight measurements)
 - Recording ECOG Performance Status and Karnofsky Performance Status
 - Vital signs (including temperature, pulse rate, respiration rate and blood pressure)
 - Concomitant medication assessment (including those medications taken within 30-days prior to implantation)
 - Hematology profile (CBC with differential WBC and platelet count)
 - Coagulation profile (PT, PTT and INR)
 - Erythrocyte sedimentation rate
 - Comprehensive chemistry profile (CO₂, sodium, potassium, chloride, creatinine, BUN, glucose, calcium, total protein, albumin, total bilirubin, alkaline phosphatase, AST and ALT), glucose, GGT, LD
 - Urinalysis, and if clinically indicated, a 24-hour urine collection
 - Amylase, lipase
 - Serum direct bilirubin

- Immunoglobulin levels
- Tumor markers: CEA, CA 19-9, CA 125.
- Circulating Tumor Cell levels (if possible)
- Baseline ECG within 28 days of implantation
- PA/lateral chest x-ray (within 28 days of implantation). If chest x-ray results indicate potential thoracic cancer-related abnormalities, then perform a non-contrast chest CT (within 21 days of implantation).
- PET-CT of whole body or MRI of the abdomen and pelvis (within 21 days prior to receiving first implant)
- Radionuclide bone scan (only if medically indicated)
- Disease assessment (baseline tumor assessment from x-rays, CT/MRI, and bone scans)
- C-reactive protein
- Hepatitis B, C, E
- HIV
- Cellular immune function
 - T cells
 - Cytokine production
 - B cells
 - Antibodies to common bacteria and viruses (diphtheria, tetanus, mumps, rubella)
 - Quantitative IgG subclass determinations
 - NK cells count (CD16)
- Ecotropic murine leukemia virus (e-MuLV) (PCR-based assay)
- Murine allergen skin test, including positive and negative controls
- Pregnancy test for females of childbearing potential

5.1.2 Decision to Proceed with First Implantation

The medical/surgical decision to proceed to the first implantation will be made based on the overall clinical assessment (physical examination, vital signs, EKG, routine blood work, status of the subject's cancer, availability of alternate treatment modalities, and the absence of evidence of allergic reaction to mouse antigens). Much of the above testing, such as that for immunological function, will not be available by Day -1, but the samples for testing will be obtained prior to therapy and the results of the testing is intended to establish a reliable baseline for research purposes and would not have an impact on the clinical decision-making process.

5.1.3 Study Day -28 to Study Day -1:

From Study Day -28 to Study Day -1, all test results that are available will be collected and reviewed. If the data indicate that there are no contraindications to proceeding, on Day 0 (Day of Implantation), RENCA macrobeads (8 per kg body weight) will be implanted intraperitoneally.

5.1.4 Visit 1 / Study Day 0:

The day of implantation will be protocol Implant 1 / Study Day 0. RENCA macrobeads (8 per kg body weight) will be implanted intraperitoneally. The subject will receive a small abdominal incision(s) utilizing laparoscopy, when possible, under general or local anesthesia, as indicated, and under sterile conditions in the operating rooms of New York Presbyterian Hospital. The location of the incision(s) will be at the surgeon's discretion. Standard procedures call for the administration of 1 gm of cefazolin just prior to surgery as antibiotic prophylaxis, unless otherwise indicated by the subject's medical history (allergies or other condition).

Standard surgical procedures and three-layer closure of the abdominal wound, if possible, will be carried out. Vital signs will be monitored as per routine for a post-laparoscopy subject and according to any special needs individual subjects may have. Assuming that the subject's post-surgical condition is stable (as defined by standard post-operative criteria) and that the subject is taking oral fluids and soft foods at a minimum, the subject will be discharged from surgical recovery room to either home care or hospital confinement as soon as medically indicated which may be same day as implantation. Any other blood drawing or procedures will be those dictated by optimal clinical care.

If deemed medically and surgically safe by the operating surgeon, one or more biopsies of tumor mass will be taken during this procedure. Fresh frozen tissue and fixative-treated tissue will be sent to the laboratory for immunohistochemical and gene array analysis to determine baseline tumor histopathology and gene expression patterns.

5.1.5 Home Care:

Post-surgical home care requirements are expected to be minimal. Medical and wound care regimens will be carried out as individually prescribed by the investigators and appropriate physicians directly involved in the subject's care. The subject will complete a daily log of activity (ADL) and a general symptom checklist (defined subjectively), but with special emphasis on appetite, abdominal symptoms such as pain or cramping, bowel movements, urination (frequency,

dysuria), and pain medication requirements. Both the subject and her/his family members will be trained in the simple vital sign measurements and the filling in of the activity log/assessment and symptom checklist. Vital signs will be measured twice daily at 8am and 8pm for the first month after implantation, then once a day for the next two months. The investigators may modify this schedule, if the clinical circumstances demand such modification. Subject and family training will take place prior to macrobead implantation, with a review prior to discharge after implantation.

A critical safety parameter will be the determination of the presence or absence of antibody to murine viruses, including mouse leukemia virus (MuLV), as well as viral titers for murine viruses known to be infective for humans. The published literature and the co-culture experiments carried out in our laboratory do not indicate that MuLV can infect human cells. Furthermore, the RENCA cells used to prepare the cancer macrobead have tested negative for other known murine viruses (Charles River panel of 18 murine viruses). In addition, none of the thirty-one (31) subjects treated to date in the Phase I study have shown any evidence of viral infection associated with the macrobeads. Nonetheless, this protocol includes laboratory and clinical monitoring for any such viral transmission. If there is any laboratory or clinical evidence indicating or suggesting a viral infection with MuLV, all family members having direct physical contact with that subject will also be assessed for the identified murine virus or for any clinical or laboratory evidence of a known or unknown viral infection. Virological monitoring of all staff in contact with the subject will be carried out at that time as well. It should be emphasized again that there has been no evidence of such transmission or infection in the Phase I trial.

5.1.6 Visit 2, Study Day 14 ± 3 days:

A brief examination including the parameters listed below will be performed. Assuming that the wound examination is satisfactory, all sutures/staples will be removed by the surgeon who performed the laparoscopy or appropriate surrogate. In addition, the Investigator will also examine the subject.

The following data will be obtained:

- Vital signs with weight
- Physical examination with brief neurological exam
- CBC with differential WBC, platelet count
- Coagulation profile (PT, PTT and INR)
- Erythrocyte sedimentation rate
- Comprehensive Metabolic Panel with LD, GGT, CRP, direct bilirubin

- Cytokine panel
- CEA, CA 19-9, CA 125
- Circulating Tumor Cell Levels
- Monitoring of adverse events and concomitant medications
- Global clinical assessment
- Quality of life scale
- ECOG and Karnofsky Performance status rating
- Pain scale, if appropriate

5.1.7 Visit 3, Study Day 30 ± 5 days:

The following data will be obtained:

- Vital signs with weight
- Physical examination with brief neurological exam
- CBC with differential WBC, platelet count
- Coagulation profile (PT, PTT and INR)
- Erythrocyte sedimentation rate
- Comprehensive Metabolic Panel with LD, GGT, CRP, direct bilirubin
- Cytokine panel
- CEA, CA 19-9, CA 125
- Circulating Tumor Cell Levels
- Ecotropic murine leukemia virus tests
- Monitoring of adverse events and concomitant medications
- Global clinical assessment
- Quality of life scale
- ECOG and Karnofsky Performance status rating
- Pain scale, if appropriate

5.1.8 Visit 4, Study Day 60 ± 5 days:

The following data will be obtained:

- Vital signs with weight
- Physical examination with brief neurological exam
- CBC with differential WBC, platelet count
- Coagulation profile (PT, PTT and INR)
- Erythrocyte sedimentation rate
- Comprehensive Metabolic Panel with LD, GGT, CRP, direct bilirubin
- Cytokine panel
- CEA, CA 19-9, CA 125

- Circulating Tumor Cell Levels
- Monitoring of adverse events and concomitant medications
- Global clinical assessment
- Quality of life scale
- ECOG and Karnofsky Performance status rating
- Pain scale, if appropriate

5.1.9 Visit 5, Study Day 90 ± 5 days:

The following data will be obtained:

- Vital signs with weight
- Physical examination with brief neurological exam
- CBC with differential WBC, platelet count
- Coagulation profile (PT, PTT and INR)
- Erythrocyte sedimentation rate
- Comprehensive Metabolic Panel with LD, GGT, CRP, direct bilirubin
- Cytokine panel
- CEA, CA 19-9, CA 125
- Circulating Tumor Cell Levels
- Ecotropic murine leukemia virus (immunology, PCR) tests
- Monitoring of adverse events and concomitant medications
- Global clinical assessment
- Quality of life scale
- ECOG and Karnofsky Performance status rating
- Pain scale, if appropriate
- MRI if needed
- PET-CT scan of whole body
- Pregnancy test, females of childbearing potential only
- Urinalysis
- EKG
- CXR
- Cellular immune function [T cells, B cells, Antibodies to common bacteria and viruses (diphtheria, tetanus, mumps, rubella), Quantitative IgG subclass determinations, NK cells count (CD16)]
- Immunoglobulin Levels (IgA, IgG, IgE, IgM)
- Murine allergen skin test, including positive and negative controls

Decision to Proceed with Second Implantation

All available information from the imaging studies, tumor marker and other laboratory findings, as well as physical examination findings and quality of life measurements from Visit 5 will be reviewed to determine if a subject is cleared for the proposed anesthesia and second implantation of macrobeads. Assuming the subject is cleared, the second implantation will proceed as soon as possible.

5.1.10 Visit 6, Implant 2 / Study Day 0:

Beginning 3 months after the first implant, the subject will be scheduled for a second implant of the cancer macrobeads at a dosage of 8 macrobeads per kilogram body weight. Assuming that the subject's post-surgical condition is stable (as defined by standard post-operative criteria) and that the subject is taking oral fluids and soft foods at a minimum, the subject will be discharged to home care as soon as medically indicated which may be the same day as implantation.

If deemed medically and surgically safe by the operating surgeon, one or more biopsies of tumor mass will be taken during this procedure. Fresh frozen tissue and fixative-treated tissue will be sent to the laboratory for immunohistochemical and gene array analysis to determine any changes in tumor state that may have been the result of exposure to the cancer macrobeads.

5.1.11 Visit 7, Implant 2 / Study Day 14 ± 3 days:

A brief examination including the parameters listed below will be performed. Assuming that the wound examination is satisfactory, all sutures/staples will be removed by the surgeon who performed the laparoscopy or appropriate surrogate. In addition, the Investigator will also examine the subject.

The following data will be obtained:

- Vital signs with weight
- Physical examination with brief neurological exam
- CBC with differential WBC, platelet count
- Coagulation profile (PT, PTT and INR)
- Erythrocyte sedimentation rate
- Comprehensive Metabolic Panel with LD, GGT, CRP, direct bilirubin

- Cytokine panel
- CEA, CA 19-9, CA 125
- Circulating Tumor Cell Levels
- Monitoring of adverse events and concomitant medications
- Global clinical assessment
- Quality of life scale
- ECOG and Karnofsky Performance status rating
- Pain scale, if appropriate

5.1.12 Visit 8, Implant 2 / Study Day 30 ± 5 days:

The following data will be obtained:

- Vital signs with weight
- Physical examination with brief neurological exam
- CBC with differential WBC, platelet count
- Coagulation profile (PT, PTT and INR)
- Erythrocyte sedimentation rate
- Comprehensive Metabolic Panel with LD, GGT, CRP, direct bilirubin
- Cytokine panel
- CEA, CA 19-9, CA 125
- Circulating Tumor Cell Levels
- Ecotropic murine leukemia virus tests
- Monitoring of adverse events and concomitant medications
- Global clinical assessment
- Quality of life scale
- ECOG and Karnofsky Performance status rating
- Pain scale, if appropriate

5.1.13 Visit 9, Implant 2 / Study Day 60 ± 5 days:

The following data will be obtained:

- Vital signs with weight
- Physical examination with brief neurological exam
- CBC with differential WBC, platelet count
- Coagulation profile (PT, PTT and INR)
- Erythrocyte sedimentation rate
- Comprehensive Metabolic Panel with LD, GGT, CRP, direct bilirubin
- Cytokine panel
- CEA, CA 19-9, CA 125

- Circulating Tumor Cell Levels
- Monitoring of adverse events and concomitant medications
- Global clinical assessment
- Quality of life scale
- ECOG and Karnofsky Performance status rating
- Pain scale, if appropriate

5.1.14 Visit 10, Implant 2 / Study Day 90 ± 5 days:

The following data will be obtained:

- Vital signs with weight
- Physical examination with brief neurological exam
- CBC with differential WBC, platelet count
- Coagulation profile (PT, PTT and INR)
- Erythrocyte sedimentation rate
- Comprehensive Metabolic Panel with LD, GGT, CRP, direct bilirubin
- Cytokine panel
- CEA, CA 19-9, CA 125
- Circulating Tumor Cell Levels
- Ecotropic murine leukemia virus (immunology, PCR) tests
- Monitoring of adverse events and concomitant medications
- Global clinical assessment
- Symptoms rating/severity assessment
- Quality of life scale
- ECOG and Karnofsky Performance status rating
- Pain scale, if appropriate
- MRI if needed
- PET-CT scan of whole body
- Pregnancy test, females of childbearing potential only
- Urinalysis
- EKG
- CXR
- Cellular immune function [T cells, B cells, Antibodies to common bacteria and viruses (diphtheria, tetanus, mumps, rubella), Quantitative IgG subclass determinations, NK cells count (CD16)]
- Immunoglobulin Levels (IgA, IgG, IgE, IgM)
- Murine allergen skin test, including positive and negative controls

Decision to Proceed with Third Implantation

All available information from the imaging studies, tumor marker and other laboratory findings, as well as physical examination findings and quality of life measurements from Visit 10 will be reviewed to determine if a subject is cleared for the proposed anesthesia and third implantation of macrobeads. Assuming the subject is cleared, the third implantation will proceed as soon as possible.

5.1.15 Visit 11, Implant 3 / Study Day 0:

Beginning 3 months after the second implant, the subject will be scheduled for a third implant of the cancer macrobeads at a dosage of 8 macrobeads per kilogram body weight. Assuming that the subject's post-surgical condition is stable (as defined by standard post-operative criteria) and that the subject is taking oral fluids and soft foods at a minimum, the subject will be discharged to home care as soon as medically indicated which may be same day as implantation.

If deemed medically and surgically safe by the operating surgeon, one or more biopsies of tumor mass will be taken during this procedure. Fresh frozen tissue and fixative-treated tissue will be sent to the laboratory for immunohistochemical and gene array analysis to determine any changes in tumor state that may have been the result of exposure to the cancer macrobeads.

5.1.16 Visit 12, Implant 3 / Study Day 14 ± 3 days:

A brief examination including the parameters listed below will be performed. Assuming that the wound examination is satisfactory, all sutures/staples will be removed by the surgeon who performed the laparoscopy or appropriate surrogate. In addition, the Investigator will also examine the subject.

The following data will be obtained:

- Vital signs with weight
- Physical examination with brief neurological exam
- CBC with differential WBC, platelet count
- Coagulation profile (PT, PTT and INR)
- Erythrocyte sedimentation rate
- Comprehensive Metabolic Panel with LD, GGT, CRP, direct bilirubin
- Cytokine panel
- CEA, CA 19-9, CA 125

- Circulating Tumor Cell Levels
- Monitoring of adverse events and concomitant medications
- Global clinical assessment
- Quality of life scale
- ECOG and Karnofsky Performance status rating
- Pain scale, if appropriate

5.1.17 Visit 13, Implant 3 / Study Day 30 ± 5 days:

The following data will be obtained:

- Vital signs with weight
- Physical examination with brief neurological exam
- CBC with differential WBC, platelet count
- Coagulation profile (PT, PTT and INR)
- Erythrocyte sedimentation rate
